### **5.2.3. Analyses for Categorical Endpoints**

NA.

### **5.2.4. Analyses for Time-to-Event Endpoints**

NA.

## **5.3. Methods to Manage Missing Data**

### **5.3.1. Efficacy Data**

The primary analysis will use the primary estimand continuous endpoint set. For each landmark analysis (eg, cross sectional analysis by week) missing data, except missing due to COVID-19 pandemic, will be imputed using a control based imputation method. PROC

MI will first be called at the visit and a control based method (implemented with the MNAR option) will impute missing vehicle observations under the assumption data are missing at random (MAR) and impute missing treatment observations assuming they are similar to corresponding vehicle patients.

Summaries of continuous data will use the observed data only and no additional considerations are needed.

Analysis of binary data will use the Secondary Estimand Categorical Endpoint Set. This dataset by definition has no missing data since all missing values, except missing due to COVID-19 pandemic, will have been set to a non-responder. Summaries will use the Observed Efficacy Set and will report results on an observed case (OC) basis.

If a subject misses a visit due to COVID-19, he/she will be excluded from the analysis for that visit; If a subject discontinues treatment or withdraws from the study due to COVID-19, he/she will be excluded from the analyses after the treatment discontinuation visit or study withdrawal visit, respectively.

CCI

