Treated area identified on Day 1 should be continued to be treated even if substantial improvement or clearing of AD or psoriasis occurs. The reason for maintaining IP treatment areas the same as identified at Day 1 is to understand the efficacy, systemic safety, and local tolerability of PF-07038124 ointment when applied to for 6 weeks in participants with mild or moderate AD or psoriasis.

Post Day 1, any new AD or psoriasis on treatment-eligible areas identified by the participant or caregiver(s) should also be treated with the IP. Decision to apply the IP to new eligible areas should be made following assessment by the Investigator or his/her designee. An unscheduled visit for assessment of the new lesion may be required at the discretion of the investigator. Body map will be updated, and IP need will be re-assessed at every site visit during the treatment period. If the total, treatable BSA exceeds 20% (AD) or 15% (psoriasis) during the six-week treatment period, the participant will still remain eligible for the study, given that the total, treatable BSA does not exceed 22% (for AD) or 16.5% (for psoriasis). If the total, treatable BSA exceeds 22% (AD) or 16.5% (psoriasis), the Sponsor may decide to discontinue the participant.

Participants and/or caregivers will be instructed not to wipe investigational product off the skin, avoid applying an occlusive dressing to the treated areas, and refrain from swimming or bathing/washing the treated areas within 4 hours after application.

Under no circumstances will the investigational drug application regimen be modified (eg, frequency of application increased or reduced, not stopped, or the application rate [target 3 mg/cm²] increased or reduced) during the study. Temporary discontinuation of investigational drug may be appropriate under some circumstances (eg, surgery, non-serious infections) and should be discussed with the Medical Monitor (or designee) preferably prior to temporary discontinuation of investigational drug.

Study intervention administration details will be recorded on the CRF.

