9.4.1. Efficacy Analyses for AD

Endpoint	Statistical Analysis Methods
Primary: Percent Change from Baseline EASI at Week 6	A landmark analysis using analysis of covariance of percent change from baseline in EASI, adjusting for the baseline EASI score, to estimate the effect of the initially randomized treatment in the absence of prohibited medication regardless of treatment compliance. The analysis will use the mITT analysis set. Missing data due to any cause including censoring due to initiation of prohibited medication will be imputed using the corresponding vehicle arm, missing data in a vehicle arm will be imputed using data from the vehicle arm assuming data are missing at random (MAR). The analysis will combine the results from the multiple imputations using Rubin's rule as implemented in SAS PROC MIANALYZE.
Secondary: IGA Response at Week 6	A landmark analysis of the composite endpoint; achieving IGA without prohibited medication, while remaining on study and providing data. The analysis will use the mITT analysis set. Based on the definition of the composite endpoint all participants in the mITT set will have a response for all visits (ie, there is no missing data). The proportions responding and

Endpoint	Statistical Analysis Methods
	the corresponding risk difference comparing active treatment arm to vehicle group will be analyzed using the unconditional exact method; the risk differences and the corresponding 2-sided unconditional exact 90% confidence intervals will be computed using Chan and Zhang (1999) ¹⁶ method.

CCI

Other continuous secondary endpoints at time points specified in the SoA including change from baseline EASI, will be analyzed as described for the primary estimand along with descriptive statistics and possibly graphical displays.

Other binary secondary endpoints at time points specified in the SoA including, CCI EASI 75, CCI IGA of clear or almost clear will be analyzed as described for the secondary estimand along with descriptive statistics and possibly graphical displays.

CCI

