### **3.2. Secondary Endpoint(s)**

#### **For AD:**

- *Proportion of participants achieving IGA score of clear (0) or almost clear (1) (on a 5-point scale) and a reduction from baseline of  $\geq 2$  points at Week 6 and other study visit time points specified in the SoA.*
- *Proportion of participants achieving EASI 75 (75% improvement from baseline) at study visit time points specified in the SoA.*
- *Proportion of participants having  $\geq 4$  points of reduction in weekly averages of Peak Pruritus Numerical Rating Scale (PP-NRS) from baseline at study visit time points specified in the SoA.*
- *Change from baseline in EASI total score at study visit time points specified in the SoA.*
- *Proportion of participants achieving IGA score of clear (0) or almost clear (1) at study visit time points specified in the SoA.*
- *Percent change from baseline in affected Body Surface Area (BSA) at study visit time points specified in the SoA.*
- *Incidence of treatment emergent adverse events (AEs) and serious adverse events (SAEs), clinically significant changes in vital signs, electrocardiogram (ECG), and laboratory tests.*
- *Incidence of severity grades in skin tolerability at times indicated in SoA.*

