**Table 2. C-SSRS Mapped to C-CASA - Suicidality Events and Codes**

| C-CASA Event Code | C-CASA Event                                 | C-SSRS Response   |
|--------------------------|---|--|
| 1                        | Completed suicide                                   | As captured in the safety database   |
| 2                        | Suicide attempt                                     | “Yes” on “Actual Attempt”  |
| 3                        | Preparatory acts towards imminent suicidal behavior | “Yes” on any of the following: 
 
• “Aborted attempt”, or
 
• “Interrupted attempt”, or
 
• “Preparatory Acts or Behavior”
 
  |
| 4                        | Suicidal ideation                                   | “Yes” on any of the following: 
 
• “Wish to be dead”, or
 
• “Non-Specific Active Suicidal Thoughts”, or
 
• “Active Suicidal Ideation with Any Methods (Not Plan) without Intent to Act”, or
 
• “Active Suicidal Ideation with Some Intent to Act, without Specific Plan”, or
 
• “Active Suicidal Ideation with Specific Plan and Intent”
 
 |
| 7                        | Self-injurious behavior, no suicidal intent         | “Yes” on “Has subject engaged in Non-suicidal Self-Injurious Behavior?”  |

#### Appendix 4. Sample SAS Code for Estimand 1

```
libname c3941002 "/Volumes/app/..... /data_vai" ;
```

```
data ps;
```

```
    set c3941002.adps;
```

```
run;
```

```
data look;
```

```
    set ps;
```

```
    where param = "EASI02-Total Sum" and viswin ne .;
```

```
    keep subjid param paramn avisit age sex trta viswin visit xviswin aval base chg pchg trtan;
```

```
run;
```

```
**example data for a single visit;
```

```
**created from systemic study ;
```

```
**ignore values, only used for illustration;
```

```
**data already has one record per subject per visit even if
```

```
**data is missing. Proc Mi needs missing values in order to impute;
```

```
data ex1;
```

```
    set look;
```

```
      where upcase(avisit)='WEEK 6';  
regimen = "QD";  
if trtan = 1 then dose=0;  
if trtan = 2 then dose=0.01;  
      keep subjid dose regimen chg aval base;  
  
run;  
  
proc means data=ex1;  
      class regimen dose;  
      var chg aval;  
  
run;  
  
proc sort data=ex1 out=ex2;  
      *data must be sorted by regimen before usin proc mi;  

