      by regimen dose;  
  
run;  
  
*imputing aval=observed so range of endpoint 0-72 can be included in;  
  
*mi procedure;  
  
proc mi data=ex2 seed=1022 nimpute=1000 out=outimp max=72 min=0;  
      by regimen;  
      class dose;
```

```
monotone reg(aval= base/details);  
mnar model( aval/modelobs = (dose="0"));  
var base aval;
```

```
run;
```

```
proc univariate data=outimp;
```

```
var aval;
```

```
histogram ;
```

```
run;
```

```
data outimp1;
```

```
set outimp;
```

```
chg = aval - base;**calculate chg from baseline
```

```
run;
```

```
proc sort data = outimp1 out = outimp2;
```

```
by _imputation_ regimen dose subjid;
```

```
run;
```

```
proc mixed data=outimp2;
```

```
by _imputation_ ;  
class dose regimen;  
model chg = base dose*regimen;  
lsmeans dose*regimen/ diff alpha=.1 ;  
ods output diffs=diffs lsmeans=lsmeans;
```

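### Missing Week 6 vehicle scores are imputed from baseline alone, although Week 1, 2 and 4 scores are collected; if vehicle drop-outs were doing worse, the treatment difference is understated

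*SAP*

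**What the plan says.** Protocol 9.4.1 sets the rule for the vehicle arm: "missing data in a vehicle arm will be imputed using data from the vehicle arm assuming data are missing at random (MAR"). Protocol 9.4.2 repeats it for psoriasis. Neither names the predictors.

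SAP 5.3.1 runs the imputation one visit at a time. PROC MI "will first be called at the visit and a control based method (implemented with the MNAR option) will impute missing vehicle observations" under MAR, and the same step will "impute missing treatment observations assuming they are similar to corresponding vehicle patients". No predictors are listed here either.

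They appear only in SAP Appendix 4. The data are cut with "where upcase(avisit)='WEEK 6", the imputation statement is "monotone reg(aval= base/details", the variable list holds only the baseline and Week 6 scores, and the model is fitted on observed vehicle participants for both arms.

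The interim data exist. The Schedules of Activities (Protocol 1.3.1 and 1.3.2) collect EASI or PASI at Weeks 1, 2, 4 and 6, at follow-up and at early termination. SAP 3.2 uses them for secondary endpoints, for example "Change from baseline in EASI total score at study visit time points specified in the SoA".

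Three other provisions bear on the point. SAP Appendix 2.1 counts any score from Day 37 to Day 57 as Week 6. SAP 6.1.1.2 plans a supplementary MMRM under MAR. SAP 5.3.1 excludes data missing because of COVID-19 instead of imputing them.

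**The concern.** MAR given baseline alone means that, at a given baseline score, whether a vehicle participant has a Week 6 score is unrelated to how the disease went in between. The plan itself gives reasons to doubt this. Scores after prohibited medication are set to missing (Protocol 9.1.1 and 9.1.2), and a flare is a plausible reason to take such medication. Protocol 6.1.1.1 adds that once treatable BSA passes 22% (AD) or 16.5% (psoriasis), "the Sponsor may decide to discontinue the participant". Treatable BSA cannot fall below its Day 1 value (Protocol 8.1.2.3 and 8.1.4.3), so only new lesions can trigger that rule.

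A vehicle participant whose score rose at Weeks 2 and 4 and who then left would be imputed as a typical vehicle completer. The vehicle mean is also the donor for missing active scores, so an error there reaches both arms. At stake is a primary contrast resting on about 21 (AD) or 12 (psoriasis) completers per arm.

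**Working it through.** **Inputs from the documents.** AD: difference 50, SD 48, 28 randomized and 21 evaluable per arm, two-sided 0.05, about 90% power (Protocol 9.2.1). Psoriasis: difference 4.5, SD 4.2, 16 randomized and 12 evaluable per arm, two-sided 0.1, about 80% power (Protocol 9.2.2). Drop-out is 25% in both.

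**The plan's figures reproduce.** 28 × 0.75 = 21 and 16 × 0.75 = 12. For AD the standard error is 48 × √(2/21) = 14.81, and 50/14.81 − 1.96 = 1.415, giving 92.2% by the normal approximation and 90.9% by the noncentral t. Psoriasis gives 81.5% by the noncentral t.

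**Inputs the documents do not give.** There is no drop-out rate or reason by arm, no correlation between visits, and no gap G between vehicle completers and vehicle drop-outs at the same baseline. I take G as 0.25, 0.5 and 1 SD, that is 12, 24 and 48 EASI percentage points.

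**Closed form.** Let C be the vehicle completer mean, A the active completer mean, and dv and da the drop-out rates in the vehicle and active arms.
- True vehicle mean: C + dv·G. Baseline-only imputation returns C, too favourable by dv·G.
- Under copy-to-vehicle, the correct difference is (1 − da)(A − C − dv·G); the planned method gives (1 − da)(A − C).
- Error, toward zero: dv × (1 − da) × G.

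With dv = da = 0.25 the multiplier is 0.25 × 0.75 = 0.1875.

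| G | Vehicle mean too favourable by | Difference understated by | Power at 21/arm, normal approximation |
|---|---|---|---|
| 0 | 0 | 0 | 92% |
| 12 | 3 | 2.25 | 90% |
| 24 | 6 | 4.5 | 87% |
| 48 | 12 | 9 | 79% |

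The power column subtracts the error from 50 inside the plan's own calculation. It is indicative only, because that calculation does not include copy-to-vehicle dilution. For psoriasis the same fractions of the SD (G = 1.05, 2.1, 4.2) give 0.2, 0.4 and 0.8 PASI points.

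**Direction.** A large-sample simulation (400,000 per arm) used assumed means of −30 (vehicle) and −80 (active), SD 48, and Week 4-Week 6 correlations of 0.5, 0.7 and 0.9. The benchmark imputes vehicle drop-outs from Week 4 and gives active drop-outs the resulting vehicle mean.

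| Who leaves | Baseline-only difference | Benchmark |
|---|---|---|
| Worst 25% on vehicle; random 25% on active | −29.8, −26.9, −23.7 | −37.5, −37.5, −37.4 |
| Worst 25% in both arms | −37.4, −37.5, −37.6 | −45.1, −48.2, −51.4 |
| Random 25% in both arms | −37.2, −37.6, −37.4 | −37.2, −37.5, −37.4 |
| Best 25% on vehicle; random 25% on active | −45.1, −48.0, −51.2 | −37.5, −37.3, −37.4 |

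The first row agrees with the closed form: at correlation 0.5 the vehicle mean is −40.2 instead of −30.0, and 10.2 × 0.75 = 7.65. Losing exactly the worst quarter is an extreme pattern. That Week 4 removes the error is by construction, since simulated drop-out depends on Week 4 alone.

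**Who is affected.** Follow-up is 28-35 days after the last dose. For it always to fall in Day 37-57, the last dose must be no earlier than 37 − 28 = Day 9 and no later than 57 − 35 = Day 22. For a last dose on Days 2-8 or 23-29 it may fall there; from Day 30 it cannot.

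**The case against.** The strongest reply is that a reader might infer more than the documents support.

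- **That early-termination scores are ignored.** Not in general. Protocol 7.1 keeps participants who stop treatment in the study, SAP Table 1 says data after drug discontinuation are not censored, and a score in Day 37-57 becomes the Week 6 value. The gap is confined to full withdrawals, scores removed after prohibited medication, and stoppers with no score in the window. This stands.
- **That the effect is understated, full stop.** The documents give no reasons or rates by arm, and the sign depends on them. If active drop-outs did as badly as vehicle drop-outs, the net error would be (dv − da) × G: zero at equal rates, and an overstatement of 1.8 to 7.2 points at 10% vehicle and 25% active drop-out. That is not the benchmark the plan states, however. SAP 2.1.1 and Protocol 9.1.2 give active drop-outs a response like that of vehicle participants.
- **That the BSA rule shows drop-outs have worse scores.** It does not. Treatable BSA retains cleared areas and counts palms and soles, which EASI and PASI exclude; discontinuation is discretionary; and no figure shows more spread on vehicle.
- **That the appendix is only sample code.** It is, but it is the only place the predictors are given, and it matches the visit-by-visit wording of 5.3.1. Its remark about illustration concerns the data values, not the model.
- **That the MMRM covers it.** It uses the interim visits, but assumes MAR in both arms and so drops the copy-to-vehicle rule. It would hint at a problem without correcting the primary estimate. The planned ANOVA sensitivity analysis only removes the baseline covariate.

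In the scenario of concern the error is also conservative: it costs power and does not create a false positive.

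**Conclusion.** As specified, vehicle MAR is conditional on baseline alone, and informative scores already in hand go unused. If vehicle participants without a usable Week 6 score were worse than completers with the same baseline, the AD difference is understated by about 2 to 9 points for G of 12 to 48. Against the 37.5 points (0.75 × 50) that copy-to-vehicle would give at the planned effect, this is 6% to 24%; against the standard error of 14.81, it is 0.15 to 0.61.

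Those sizes rest on the assumed G, on 25% imputed in each arm, and on active drop-outs taking the full vehicle mean. COVID-19 exclusions and in-window scores would reduce the imputed fraction. An unconditional claim of understatement is not supported: the error is zero if drop-out is unrelated to response and reverses if vehicle participants leave because they improved. The recommendation does not need the sign to be known; it is a cheap improvement to the primary analysis.

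**What to change.** In SAP 5.3.1 and Appendix 4, specify two steps and name the predictors.

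1. **Vehicle arm.** Impute under MAR by sequential monotone regression on baseline, Week 1, Week 2 and Week 4, then Week 6, filling intermittent gaps first. For psoriasis, with about 12 completers, use a reduced set such as baseline plus Week 4. State how early-termination scores outside Day 37-57 are used, including those in the Day 19-25 window, which has no scheduled visit. Confirm that scores before prohibited medication are kept: Protocol 9.1.1 removes only later observations, while SAP 2.1.1 can be read as removing all of that participant's scores.
2. **Active arm.** Keep the control-based rule, using the completed vehicle data within each imputation, and state which pre-drop-out scores the step conditions on.

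The second statement matters. Adding the interim visits to the present single call would also condition active drop-outs on their own on-treatment scores. In the simulation with random drop-out, that alone moved the difference from −37.2 to −43.4 (correlation 0.5) and from −37.4 to −48.6 (correlation 0.9). Conditioning the active step on baseline only keeps the assumption in the current code.

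The cost is a few lines of SAP text and code and no new data. The downside is a slightly larger imputation model in a small vehicle arm.

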9.1. Estimands and Statistical Hypotheses

9.1.1. Estimands for AD

The primary estimand will be the population average treatment effect on percent change from baseline in EASI score relative to vehicle at 6 weeks in the absence of prohibited medication without regard to compliance. All observations after the initiation of prohibited medication will be set to missing. Missing data from all causes, including post-randomization prohibited medication use will be imputed in the PF-07038124 arms using a copy to control method (ie, missing data in 0.01% QD regimen will be imputed from the distribution of participants on QD vehicle). Participants with inadequate compliance will have their recorded EASI scores used as is in the analysis. The population-based treatment effect will be the differences in the mean change from baseline in treatment arm compared to the vehicle.

The secondary estimand will be the estimated population average treatment effect on the rates of IGA response (participants with a score of 0 or 1 and a 2 point or greater decrease from baseline) at Week 6 relative to vehicle without regard to compliance with IP in the absence of prohibited medication. This is a composite estimand where success is defined as achievement of an IGA response as defined above while remaining on study, providing data and not taking prohibited medication; lack of compliance or adverse events will not be counted as a failure. The population-based treatment effect will be the differences in the proportions of success in each treatment arm compared to the corresponding vehicle. EASI 75 and other EASI scores will be treated in a similar manner.

All other secondary continuous clinical endpoints will be analyzed using the primary estimand, while all other secondary categorical clinical endpoints will be analyzed using the secondary estimand described above. CCI

Other estimands may be used for some of the primary and secondary endpoints as a means to examine the robustness of the results and to compare to available literature as needed. Details of these analyses will be presented in the Statistical Analysis Plan (SAP).

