**Table 1. Summary of Major Changes in SAP Amendments**

| SAP Version | Change   | Rationale   |
|-------------|--|---|
| 1           | Not Applicable   | Not Applicable  |
| Amendment   | Section 3

Adding IGA/PGA response at other timepoints besides week 6 as secondary endpoint

CCI [REDACTED]        | Longitudinal profile of IGA/PGA response are of clinical importance

CCI [REDACTED]           |
|             | Section 6.1.1 and 6.2.3.1

Data collected for subjects after early drug discontinuation will not be censored.            | Estimand is irrespective of non-compliance.   |
|             | Section 6.1.1.1 and 6.2.3.1

Number of multiple imputation is changed from 100 to 1000                                   | To increase the precision of variance estimate of the treatment effect based on multiple imputation |
|             | Section 6.2.3

For ANCOVA analysis at week 6 for secondary endpoints, multiple imputation will be used for missing data. | To be consistent with primary endpoint analysis.  |

|  |                          |  |
|--|--------------------------|--|
|  | Section 6.2.3

CCI |  |
|--|--------------------------|--|

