### 2.1.1. Primary Estimand(s)

The primary estimands of this study will use the treatment policy strategy and estimate the treatment difference without the benefit of additional prohibited medications during treatment and regardless of participant compliance with the IP dosing. This estimand (Estimand 1) for AD and Psoriasis are defined according to the primary objectives and are in alignment with the primary endpoints.

For AD, it includes the following 4 attributes:

- Population: Participants with mild or moderate AD as defined by the inclusion and exclusion criteria; without the benefit of receiving prohibited medications during treatment and regardless of compliance.
- Variable: Percent change from baseline in EASI total score at Week 6.
- Intercurrent event(s): A) Prohibited medication – all scores in participants who receive prohibited medication post randomization will be omitted from the analysis and treated as missing scores. Missing scores will be imputed based on the assumption that participants do not benefit from the IP treatment. B) Withdrawal and all other events leading to missing data will be treated similarly assuming participants have efficacy values similar to control participants. C) Inadequate compliance – participants data will be used as recorded.
- Population-level summary: The percent change from baseline mean difference between treated and vehicle in EASI score.

For Psoriasis, it includes:

- Population: Patients with mild to moderate plaque psoriasis as defined by the inclusion and exclusion criteria of the study who do not take prohibited medications during treatment and regardless of compliance.
- Variable: Change from baseline PASI score at Week 6.
- Intercurrent events: A) Prohibited medication – all scores in participants who receive prohibited medication post randomization will be omitted from the analysis and treated as missing scores. Missing scores will be imputed based on the assumption that participants do not benefit from the IP treatment. B) Withdrawal and all other events leading to missing data will be treated similarly as in A). C) Inadequate compliance – participants data will be used as recorded.
- Population-level summary: The mean difference between treated and vehicle control arms of the change from baseline PASI score.

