#### 6.2.1.1. Main Analysis

- Estimand strategy: Secondary estimand ([Section 2.1.2](#)) use a composite endpoint strategy. This estimand is intended to provide an estimate of the treatment effect in the absence of prohibited medication use in a population that may or may not be fully compliant with the treatment.
- Analysis set: mITT ([Section 4](#)) using data prepared in the description of the Secondary Estimand Categorical Endpoint Set.
- Analysis methodology: Risk differences will be analyzed using the method of Chan and Zhang (1999). Confidence Interval of binomial proportion will be reported using Blyth-Still-Casella method.
- Intercurrent events and missing data: These have been accounted for in the preparation of the Secondary Estimand Categorical Endpoint Set ([Section 5.3](#)). This prepared data set has no missing values.
- Proportions, risk differences and 90% confidence intervals will be presented.

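### The SAP's COVID-19 rule drops scores recorded after stopping IP and leaves COVID-missing scores unimputed, which the stated estimands and the protocol do not provide for

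*SAP*

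**What the plan says.** SAP 5.3.1 sets three COVID-19 rules.

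- **Imputation exemption.** For continuous endpoints, "missing data, except missing due to COVID-19 pandemic, will be imputed using a control based imputation method". The same exception is made to the non-responder rule for binary endpoints.
- **Missed visit.** "If a subject misses a visit due to COVID-19, he/she will be excluded from the analysis for that visit".
- **Stopping.** A participant who discontinues treatment or withdraws from the study because of COVID-19 is removed from what follows: "he/she will be excluded from the analyses after the treatment discontinuation visit or study withdrawal visit, respectively".

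The estimand sections read differently. SAP 2.1.1 states: "The primary estimands of this study will use the treatment policy strategy". It applies regardless of compliance with IP, and under inadequate compliance "participants data will be used as recorded". Withdrawal and every other event leading to missing data is handled as if the participant had control-like efficacy. SAP 2.1.2 follows the same pattern for binary endpoints, with failure in place of imputation. Neither section lists COVID-19 as an intercurrent event.

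Protocol 9.1.1 states for AD: "Missing data from all causes, including post-randomization prohibited medication use will be imputed in the PF-07038124 arms using a copy to control method". Protocol 9.1.2 covers censoring, withdrawal and other reasons in the same way for psoriasis. Protocol 9.4.1 and 9.4.2 impute missing data from any cause in the mITT set, and state that every mITT participant has a binary response at every visit.

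**The concern.** The same event is handled in opposite ways according to its attributed cause. A participant who stops IP for, say, a local reaction and is scored later has that score used. A participant who stops IP for COVID-19 and is scored on the same day has it removed. A missed Week 6 visit is control-imputed, or counted as failure, unless the reason is COVID-19, in which case the participant leaves the Week 6 analysis.

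Because the primary analysis is a Week 6 landmark ANCOVA, exclusion at Week 6 removes the participant from it altogether. The analysed set is then smaller than the mITT set named in SAP 6.1.1.1. It is selected on a post-randomisation event, and the quantity estimated is not the one in SAP 2.1.1.

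**Working it through.** **1. The design figures reproduce, so no stated figure is at fault.** Two-sample t-test power with noncentrality difference / (SD × √(2/n)):

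- AD (Protocol 9.2.1): n = 21 per arm, difference 50, SD 48, two-sided 0.05. 50 / (48 × √(2/21)) = 3.375 on 40 df, power 90.9% (stated about 90%).
- Psoriasis (Protocol 9.2.2): n = 12 per arm, difference 4.5, SD 4.2, two-sided 0.1. 4.5 / (4.2 × √(2/12)) = 2.62 on 22 df, power 81.5% (stated about 80%).

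**2. Can a score recorded after stopping IP reach the Week 6 analysis?** Protocol 7.1 sends a participant who definitively stops IP to the early termination visit and keeps them in the study for follow-up. The Schedule of Activities places follow-up 28 to 35 days after the last dose, with EASI and IGA (AD) or PASI and PGA (psoriasis) scored. SAP Appendix 2.1 assigns Day 37 to 57 to Week 6. For a last dose on Day d, follow-up falls on Day d + 28 to d + 35.

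- Whole range inside the window: d + 28 ≥ 37 and d + 35 ≤ 57, so d = 9 to 22.
- Part of the range inside: d + 35 ≥ 37 and d + 28 ≤ 57, so d = 2 to 8 or 23 to 29.

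So such scores can exist for a last dose on Day 2 to 29, and the COVID-19 rule removes them. Protocol 10.9.5 also foresees temporary stopping for COVID-19. SAP 5.3.1 does not separate temporary from permanent stopping, so read literally it could also exclude someone who resumes IP and attends Week 6.

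**3. Size of the difference between the two rules.** The documents give no COVID-19 count. Assume k participants per arm have COVID-missing Week 6 scores, other data are complete, and the loss is unrelated to outcome. With N per arm (28 AD, 16 psoriasis) and planned difference D:

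- exclusion: expected difference D;
- control imputation (continuous) or non-responder (binary): D × (1 − k/N).

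| Endpoint | Exclude | k = 1 | k = 2 | k = 4 |
|---|---|---|---|---|
| EASI % change, D = 50 | 50 | 48.2 | 46.4 | 42.9 |
| PASI change, D = 4.5 | 4.5 | 4.22 | 3.94 | 3.38 |
| IGA, 55% − 20% | 35 pts | 33.8 | 32.5 | 30.0 |
| PGA, 65% − 20% | 45 pts | 42.2 | 39.4 | 33.8 |

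Per active participant the continuous difference is 50/28 = 1.8 EASI percentage points or 4.5/16 = 0.28 PASI points. If scores after stopping are observed and used as recorded, the expected value lies between the two rules, depending on how much effect persists.

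**4. Does the rule cost power?** IGA, unconditional exact test (pooled z), two-sided 0.05. Applying the planned 25% dropout as non-response gives 0.75 × 55% = 41.25% and 0.75 × 20% = 15%. At 28 per arm, power is 59.2%.

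- COVID-19 losses on top of planned dropout: exclusion (n = 28 − k, same rates) gives 54.7% (k = 2) and 50.4% (k = 4). Non-responder handling (n = 28, rates × (28 − k)/28) gives 54.6% and 49.8%.
- COVID-19 losses within planned dropout: exclusion (n = 28 − k, rates 55% and 20% × 21/(28 − k)) gives 59.4% (k = 2) and 61.3% (k = 4), against 59.2% under the non-responder rule.

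Exclusion costs no power relative to the rule it replaces.

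**The case against.** **COVID-missing data are a different kind of missing.** Setting pandemic-related loss apart can be a legitimate strategy, since it may have little to do with drug or disease. This stands for truly missing scores. It does not cover discarding scores that were recorded, and the strategy still has to appear in the estimand. Protocol Section 9 lets the SAP modify the protocol. Whether this is a major change needing an amendment is a judgement, but that does not settle the conflict inside the SAP.

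**Little observed data is lost.** This stands. A reader might infer that scheduled Week 6 outcomes are discarded in general. Protocol 7.1 describes early termination and follow-up after definitive stopping, not a Week 6 visit, and scores at the discontinuation visit itself appear to be kept. The loss is mainly follow-up scores that window to Week 6.

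**Stronger readings that the documents do not support.**

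- A reader might infer a loss of precision or power. Any widening comes from outcomes being missing, and step 4 shows that exclusion gives power no lower than the non-responder rule.
- A reader might take SAP 6.2.1.1, "This prepared data set has no missing values", as a separate contradiction. It refers back to Section 5.3, where the COVID-19 exception is stated, and a set from which participants have been removed can have no missing values.
- A reader might cite the SAP's table of changes, "Data collected for subjects after early drug discontinuation will not be censored". It is a change summary tied to Sections 6.1.1 and 6.2.3.1. It points the same way but cannot by itself establish an error, and the point does not rest on it.

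**The MMRM helps.** The supplementary MMRM in SAP 6.1.1.2 assumes missing at random and would retain a COVID-affected participant's earlier visits. It does not restore scores excluded after stopping, and no listed sensitivity analysis compares the two rules for COVID-missing data.

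**Conclusion.** The conflict is in current text. SAP 5.3.1 removes scores recorded after COVID-related stopping of IP, against SAP 2.1.1 and 2.1.2. It also leaves COVID-missing scores outside imputation and the non-responder rule, against the protocol's all-cause rule and its statement that every mITT participant has a binary response. The label is wrong as written.

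The number affected is unknown and may be zero, in which case only the wording is at issue. The per-participant figures rest on the planning differences, full follow-up otherwise, and COVID-19 loss unrelated to outcome. If that last assumption fails, or the arms lose different numbers, the documents give no basis for the size or direction of the bias.

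**What to change.** 1. In SAP 5.3.1, delete the exclusion after COVID-related treatment discontinuation. Use scores recorded after such stopping, temporary or permanent, as recorded, as for any other reason for stopping.
2. For scores truly missing because of COVID-19, make 5.3.1 and the estimands agree by one of two routes:
   - apply the stated copy-to-control rule (continuous) and non-responder rule (binary), with exclusion as a sensitivity analysis; or
   - define COVID-related missingness explicitly in SAP 2.1.1 and 2.1.2, with its own handling for continuous and binary endpoints, and run the all-cause rule as the sensitivity analysis.
3. Carry the chosen rule through SAP 6.1 and 6.2. If the second route is taken, reconcile it with Protocol 9.1 and 9.4 and decide whether it is a major change needing an amendment.

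Imputing COVID-missing scores from the participant's own arm under MAR is not the automatic remedy. It also departs from copy-to-control and gives no rule for the binary composite, so it would need the same definition in the estimand.

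The cost is SAP wording, minor programming and one added sensitivity analysis, with no new data collection.
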